## 7.0 TOXICITY MANAGEMENT

### 7.1 Antiretroviral toxicity

For HIV-infected children enrolled, ART management for HIV will be managed through the subject's primary clinic. This study is not designed to initiate ART treatment for study subjects. ART regimens permitted for this study include only EFV-based regimens.

### 7.2 Artemether-lumefantrine toxicity

AL will be used to manage acute uncomplicated malaria. AL is the Ugandan first-line national regimen and would be the preferred treatment for all patients whether enrolled in this study or not. AL as a 3-day regimen is standard of care while AL as a 5-day regimen is being evaluated in this study and is a “study regimen”. Therefore, we will be assessing and recording data in relation to how participants tolerate AL. As noted in Section 1.1.8, we evaluated the impact of a cytochrome P450-inhibitor, lopinavir/ritonavir, on levels of lumefantrine in children with malaria. Day 7 levels in children on lopinavir/ritonavir-based ART had 10-fold higher day 7 levels of lumefantrine and >2-fold higher AUC, as compared to those on EFV-based ART, while exhibiting no increase in toxicity. We will, however, be recording participants tolerance of AL

using the NIH Division of AIDS Adult and Pediatric Toxicity Tables (version 2.1, March 2017; <https://rsc.tech-res.com/docs/default-source/safety/daids-ae-grading-table-mar2017.pdf>). This will be used to screen for eligibility and to evaluate adverse events for children. Study staff will receive extensive training in the identification and management of adverse events. In addition, participants will be informed by the study team about potential adverse events associated with AL and will be encouraged to present to the study clinic for all potential adverse events. Symptomatic screening for auditory AEs will be conducted at each visit. The study clinic will remain open 7 days a week so that participants may present with potential adverse events as they arise. Monitoring, reporting, and management of adverse events is described below, and will follow guidelines set forth by each respective institution.

### **7.3 Toxicity management by grade**

Alternate explanations for clinical and laboratory abnormalities will be sought. Laboratory normal values will be those provided by the clinical laboratory used for this study. For each adverse event identified as grade 3 or higher AND serious or unexpected (See Section 8.0), an adverse event report form will be completed. Adverse events will be followed until they resolve to below a grade 3.

#### **Grade 1 and 2:**

It is anticipated that some subjects may enter this study with grade 1 or 2 abnormalities already present (e.g. due to ART management). The site physicians will manage the grade 1 or 2 events according to standard practice. An adverse event report form will not be completed for events classified as grade 1 or 2, as these events are common and difficult to distinguish from common childhood illnesses.

#### **Grade 3 or 4 (non-life threatening):**

- Notify the study team.
- Repeat observation within 72 hours; notify study team of results.
- Subjects may continue taking AL pending clinic visit or repeat laboratory tests. The clinician has the option of immediately stopping the AL if the subject cannot be examined in clinic, if a repeat laboratory test cannot be performed within 72 hours, or if the clinician determines that continuation of AL is unsafe while awaiting clinic exam or test results.
- Work-up to exclude other causes.
- For all confirmed Grade 3 or 4 toxicities supported by repeat clinical exam or laboratory test results, stop AL until toxicity resolves to < Grade 3.
- If drug is restarted with resolution of toxicity and toxicity recurs on re-challenge, study drugs will be permanently discontinued. If AL is discontinued the participant will be withdrawn from the study.

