##### Adequate Clinical and Parasitological Response

- Absence of parasitemia on study Day 42, with no prior requirement for additional treatment other than the standard 6 dose regimen received at time of presentation with malaria.

- For subjects who experience treatment failure before study Day 3, PK sampling will be discontinued.

Participants from TDH or MGH who experience recurrent malaria within 42 days will be evaluated for reenrollment eligibility (see Section 4.1 and 4.2). If eligible, they will be re-enrolled into the appropriate study. For those not eligible or not willing to reenroll, effort will be made to follow them for 7 days (or longer if they remain sick) after the diagnosis of recurrent malaria. In addition, the most recent laboratory and clinical tests will be checked to assess for any grade 3 or 4 abnormalities. If present, repeat testing should be done until AE is resolved.

In the case of participant withdrawal (unless a participant cannot be located or refuses follow-up), attempt will be made to follow them until all AEs are resolved to grade 2 or below, AND until Day 7 of follow-up for treatment of current malaria episode. Attempt will also be made to obtain the Day 14 hematology and chemistry blood work for safety follow-up.

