### 9.2 Outcome Measures

#### 9.2.1 Primary outcomes

- 1) Area under the plasma concentration versus time curve for all drug analytes.
- 2) Recurrent malaria following treatment by day 42 (recrudescence or new infection)

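### A child whose AL is discontinued is withdrawn from the study, so Day 28 safety data and Day 42 recurrence status are not planned for children who did not tolerate treatment

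*Combined protocol and SAP*

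**What the plan says.** Section 7.3 (grade 3 or 4, non-life threatening) sets out a sequence.

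- After a grade 3 or 4 finding: "Repeat observation within 72 hours; notify study team of results". AL may continue meanwhile, or the clinician may stop it at once.
- If the toxicity is confirmed, the instruction is to "stop AL until toxicity resolves to < Grade 3", and the drug may be restarted.
- If the toxicity returns on re-challenge, AL is discontinued permanently. The next sentence reads: "If AL is discontinued the participant will be withdrawn from the study".

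The paragraph on life-threatening grade 4 events also requires permanent discontinuation but does not repeat the withdrawal sentence.

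Section 6.4.6 says what happens to withdrawn participants, except those who cannot be located or refuse: "attempt will be made to follow them until all AEs are resolved to grade 2 or below, AND until Day 7 of follow-up". It adds: "Attempt will also be made to obtain the Day 14 hematology and chemistry blood work for safety follow-up". The opening of Section 7.3 has a general rule without a day limit: "Adverse events will be followed until they resolve to below a grade 3".

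Section 9.2.1 makes recurrent malaria by Day 42 a primary outcome. Section 9.2.2 lists the safety of the 5-day versus the 3-day regimen first among the secondary outcomes. Section 4.3 describes 42 days of follow-up for all children around each studied episode.

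**The concern.** Stopping the drug and leaving the study are separate events, and Section 7.3 joins them. The loss is imposed by the protocol: Section 6.4.6 deals separately with families who cannot be found or who refuse, so the shortened follow-up applies to children who are reachable and willing.

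These children are selected by an outcome that arose after randomisation. They had a serious-grade toxicity and an incomplete course, so their later course cannot be assumed to match that of children who finished treatment. No section says how they enter the safety or the Day 42 analysis. If they were censored at withdrawal in a Cox model such as that of Section 9.5.2, the censoring would be related to toxicity. Section 3.2.3 also allows an intensive-study child with more than two missing PK samples to be replaced, which could make the loss less visible.

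Elsewhere the protocol keeps the two apart. Sections 6.4.6 and 6.7.1 stop only PK sampling after early failure, and Section 5.1.3 lets a child move to the population study after vomiting.

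**Working it through.** The plan states no figure on this point, so there is none to reproduce. The check has four parts.

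**1. What is lost**, from Sections 6.4.6, 6.6 and 6.10 and Appendices A and B:

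| Planned item | Provided after withdrawal? |
|---|---|
| Clinical follow-up to Day 7 | Attempted |
| Follow-up of an adverse event above grade 2 | Attempted, no day limit |
| Day 14 hematology and chemistry | Attempted |
| Visits and smears on Days 21, 28, 35, 42 | No |
| Day 28 laboratory tests | No |
| ECG on Day 28 or later (subset, up to 50 per arm) | No |
| Recurrence status to Day 42 | No |

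**2. Time at risk of discontinuation.** In the population study, doses are 12 h apart.

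- 3-day: 5 × 12 = 60 h from first to last dose.
- 5-day: 9 × 12 = 108 h.

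In the intensive study (Table 4), dose 1 falls between 11 AM and 5 PM on Day 0, and the last dose between 8 and 10 AM on Day 3 or Day 5.

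- 3-day: (72 + 8) − 17 = 63 h to (72 + 10) − 11 = 71 h.
- 5-day: (120 + 8) − 17 = 111 h to (120 + 10) − 11 = 119 h.

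If a finding at the first dose took the full 72 h to confirm, every 3-day course would be over (60–71 h). In the 5-day arm, 108 − 72 = 36 h to 119 − 72 = 47 h of dosing would remain.

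**3. Share of discontinuations in the 5-day arm.** Assumptions: 1:1 allocation and equal risk h at each dose after the first. Share = [1 − (1 − h)^9] / {[1 − (1 − h)^5] + [1 − (1 − h)^9]}. The maximum per regimen is 80 + 110 = 190 (Section 3.2).

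| h (assumed) | 3-day, of 190 | 5-day, of 190 | Share in 5-day arm |
|---|---|---|---|
| 0.1% | 0.95 (0.5%) | 1.7 (0.9%) | 64% |
| 0.5% | 4.7 (2.5%) | 8.4 (4.4%) | 64% |
| 1% | 9.3 (4.9%) | 16.4 (8.7%) | 64% |
| 2% | 18.3 (9.6%) | 31.6 (16.6%) | 63% |

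Counting total doses gives 10/16 = 62.5%. Counting dosing days gives 6/10 = 60% (intensive) or 5/8 = 62.5% (population).

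**4. Effect on the recurrence rate.** Let p be the rate among children kept and w the fraction withdrawn. If every withdrawn child recurred, the rate in all assigned children would be p(1 − w) + w, a shift of w(1 − p). Section 9.5.1 gives p = 47% on EFV-based ART and a 20-point difference, hence 27% as the lower value. The range w = 1–5% is assumed; on 80–110 episodes it is 0.8 to 5.5 episodes per arm.

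- p = 47%: 1% × 0.53 = 0.5 points; 5% × 0.53 = 2.7 points.
- p = 27%: 1% × 0.73 = 0.7 points; 5% × 0.73 = 3.7 points.

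Withdrawals in the 3-day arm partly offset this. With h = 0.5%, 47% in the 3-day arm and 27% in the 5-day arm, the shifts are 2.48% × 0.53 = 1.3 and 4.41% × 0.73 = 3.2 points, a net change of 1.9 points.

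If no withdrawn child recurred, the shift would be −wp, from −0.3 points (1% × 0.27) to about −2.4 points (5% × 0.47).

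**The case against.** The strongest reply is that few children will meet this rule. Safety laboratory tests are scheduled on Days 0, 14 and 28 only, and by Day 14 both regimens are finished. Apart from Day 0 results and unscheduled tests, only clinical grade 3 or 4 events during dosing can lead to discontinuation. Section 1.1.8 expects no added toxicity from five days of AL. This stands, and it limits the size of the problem.

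Four stronger readings are tempting, and the documents do not support them.

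- *Every stop of AL is a withdrawal.* Section 7.3 first holds the drug and allows a restart. The withdrawal sentence follows the rule on permanent discontinuation.
- *All of Days 8 to 42 is lost.* The two conditions in Section 6.4.6 are joined by AND, so an unresolved event is followed beyond Day 7, and Day 14 blood work is attempted.
- *The loss falls mainly on the 5-day arm.* The rule is the same in both arms and no rates are given. The 72 h is an upper limit: children are seen daily during dosing, and the clinician may stop AL at once. Longer dosing supports a moderate tilt, and only under the equal-risk assumption.
- *5-day AL will look safer and more effective than it is.* The documents give no recurrence or late-toxicity risk for these children, and Section 7.3 does not say what treatment follows. As shown above, the recurrence rate could move either way.

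None of this restores the missing Day 28 and Day 42 data.

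**Conclusion.** The concern holds in a limited form. The protocol ends scheduled follow-up for reachable, willing children because AL was discontinued. It thereby leaves out their Day 28 safety data and Day 42 recurrence status, and it does not say how they are analysed. The loss is related to toxicity and so potentially informative for a primary outcome and for the 5-day versus 3-day safety comparison.

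Its size is uncertain and probably small. Under the assumed 1–5% withdrawal with every withdrawn child recurring, an arm's rate moves by about 0.5–3.7 points, which does not approach the 20-point planning difference. The 60–64% share in the 5-day arm rests on equal risk per dose. The safety comparison may be the more sensitive of the two, because a handful of children can be a large part of those with severe events. This is an inexpensive improvement worth making, since data that were not collected cannot be recovered in analysis.

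**What to change.** - **Section 7.3:** replace the withdrawal sentence with a statement that discontinuing AL ends PK sampling for that episode but not study follow-up. Unless consent is withdrawn, the child keeps the scheduled visits, smears, Day 14 and Day 28 laboratory tests, ECGs where applicable, and adverse-event follow-up to Day 42. Make clear that the same applies after life-threatening grade 4 events, where the text is silent on withdrawal.
- **Section 6.4.6:** limit the shortened follow-up to children whose family withdraws consent.
- **Section 9:** state that these children are analysed in the assigned arm for safety and Day 42 recurrence, and report discontinuations by arm.

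The cost is a change of wording and a few visits for children off AL. Those visits and tests are already in Appendices A and B. When AL should be stopped, held or restarted is not changed.

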#### **Grade 4 life threatening:**

- Notify study team.
- If still receiving AL, AL should be permanently discontinued.

## 8.0 MONITORING OF ADVERSE EVENTS AND MANAGEMENT

An adverse event is defined as "unfavorable changes in health, including abnormal laboratory findings that occur in study participants during the study or within a specified period following the study". There are no "study drugs" in this study, and all therapies being studied for PK are the standard of care in Uganda and provided free of charge by the Ministry of Health outside of study participation. This study will be directly observing administration of AL (Coartem®) to participants for the treatment of malaria. Data regarding the tolerance of AL will be recorded. Study clinicians will assess patients at each scheduled and unscheduled visit to the clinic according to a standardized clinical record form using scales developed by the NIH Division of AIDS Adult and Pediatric Toxicity Tables version 2.1, March 2017. Guidelines for reporting of adverse events due to study participation provided by UCSF Human Research Protection Program and Institutional Review Board, Yale Human Investigations Committee, NICHD, Makerere University School of Medicine Research Ethics Committee (SOMREC), and the Ugandan National Council for Science and Technology will be followed as described below.

Per UCSF HRPP & IRB guidelines as found on website updated April, 2017: Adverse events which are definitely, probably, or possibly related to study procedures or study participation **AND** serious or unexpected will be reported. AEs which do not meet those criteria will be documented, referenced, and retained in the study files for follow-up. Per UCSF HRPP & IRB guidelines, the following definitions for serious or unexpected adverse events will be followed:

\*Serious Adverse Event (SAE) is any AE that results in any of the following outcomes:

- Death,
- Life-threatening adverse experience,
- Inpatient hospitalization or prolongation of existing hospitalization,
- Persistent or significant disability/incapacity,
- Congenital anomaly/birth defect, or cancer, or
- Any other experience that suggests a significant hazard, contraindication, side effect or precaution that may require medical or surgical intervention to prevent one of the outcomes listed above,
- Event occurring in a gene therapy study
- Event that changes the risk/benefit ratio of the study.

±Unexpected Adverse Event. An adverse event is defined as being unexpected if the event exceeds the nature, severity, or frequency described in the protocol, consent form and investigator brochure (when applicable). An unexpected AE also includes any AE that meets any of the following criteria:

- Results in subject withdrawal from study participation,
- Due to an overdose of study medication, or
- Due to a deviation from the study protocol

Per UNCST National guidelines March 2007: “These guidelines give criteria for prompt reporting of certain categories of adverse events to an IRC and the UNCST.” “An *adverse event* is any unfavorable and unintended sign, symptom or condition temporally associated with the administration of a health-related intervention, whether or not considered related to the intervention. The requirement to report adverse events to regulatory authorities shall not apply to events that are observed among participants who are in observational studies in which no health-related intervention is being administered.” However, for consistency, we will report adverse events which are definitely, probably, or possibly related to study procedures or study participation **AND** serious or unexpected similarly to UNCST and SOMREC.

**Table 7. Guidelines for reporting adverse events related to study participation**

Institution	Type of Adverse Events	When to Report
NICHD	
 
Definitely, Probably, or Possibly related AND Serious or Unexpected
 
	
 
Within 10 working days of awareness
 

UCSF-HRPP&IRB	
 
Definitely, Probably, or Possibly related AND Serious or Unexpected
 
	
 
Within 5 working days of awareness
 
Internal, related deaths and life-threatening events: report immediately
 

Yale-HIC	
 
Definitely, Probably or Possibly related to participation in the research AND Serious AND Unexpected (in terms of nature, specificity, severity, or frequency)
 
	
 
Within 5 days of awareness
 
Related Events not meeting prompt reporting requirements are reportable in summary form at time of continuing review
 

MU-SOMREC	
 
All Serious and Unexpected events irrespective of relationship;
 
	
 
All serious adverse events and unexpected events must be reported within 7 calendar days of awareness
 
All other reportable events should be reported within 14 calendar days
 

UNCST	
 
All Serious and Unexpected events irrespective of relationship;
 
	
 
Death and Life-threatening events within 48-hours with written report within 7-calendar days of awareness
 
All other reportable
 

		events within 15-calendar days of awareness
--	--	---

## 9.0 STATISTICAL CONSIDERATIONS

### 9.1 General Design Issues.

This is a prospective study to evaluate the PK and PD of extended dose AL in the context of EFV-based ART and in the context of HIV-uninfected children and to characterize the impact of a 5-day regimen on AL PK/PD as compared to the standard 3-day regimen; the study will be conducted in Uganda.

The current proposal will study the PK/PD of AL in HIV-infected children on EFV-based ART and HIV-uninfected children not on ART either enrolled at TDH or MGH. We will compare the PK of 5-day AL in HIV-infected children on EFV-based ART to 1) 3-day AL in HIV-infected children on EFV-based ART, and 2) 3-day AL in HIV-uninfected children. In addition, we will compare the PK of 5-day AL in HIV-uninfected children to 3-day AL in HIV-uninfected children. Comparisons will be based on an intensive PK design for AL AUC estimations in 30 to 50 subjects for each of the study groups. Study group comparisons will be controlled for age (i.e. results for HIV infected children on EFV-based ART who are 3-10 years of age, will be compared to results for HIV uninfected children who are also 3-10 years of age). The proposal will also study the impact of AL exposure on treatment outcomes and adverse events using a population PK/PD design. This will involve population PK study of up to an additional 100 HIV-infected children and 120 HIV-uninfected children.

*Although an individual child is eligible to enroll in both the intensive PK study and the population PK study for separate episodes of malaria, there is no assurance that the same child will contribute to both study components. Thus, it is possible that the total number of subjects for all groups may be as high as 380.*

### 9.2 Outcome Measures

#### 9.2.1 Primary outcomes

- 1) Area under the plasma concentration versus time curve for all drug analytes.
- 2) Recurrent malaria following treatment by day 42 (recrudescence or new infection)

#### 9.2.2 Secondary outcomes

- 1) Safety of 5-day vs 3-day AL regimens
- 2) Prevalence of gametocytemia following treatment in 3-day vs 5-day AL regimens
- 3) Weight-for-age and Height-for-age associations with PK
- 4) Diagnostic sensitivity of LAMP, HS-RDT, and microscopy for the detection of recurrent parasitemia.
- 5) Metabolomic measurements in HIV infected vs HIV uninfected children
- 6) Relationship between molecular markers of drug resistance and treatment failure

### 9.3 Nutritional Status

Using anthropometric measurements and for a secondary study aim to relate nutritional status to PK and clinical outcomes, children will be characterized as a) “stunted” but not underweight [i.e. height for age (HFA) z-score  $\leq -2$  and weight for age (WFA) z-score  $> -2$ ]; b) underweight, but not stunted (WFA z-score  $\leq -2$  and HFA z-score  $> -2$ ); or c) of normal nutritional status (WFA and HFA z-scores  $> -1$ )

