**1.1.9 Malnutrition is prevalent in African children and may impact ACT pharmacology.** Malnutrition can include a) *chronic* protein-calorie malnutrition resulting in slow linear growth (decreased height-for-age: HFA; stunting), b) *acute* protein-calorie malnutrition resulting in weight loss or slow weight gain (decreased weight-for-height: WFH; wasting) and c) micronutrient deficiencies in iron, zinc, and vitamin A that can be difficult to detect clinically. Underweight (decreased weight-for-age: WFA) status reflects the combination of *chronic and acute* protein-calorie malnutrition, and is the most clinically utilized indicator of nutritional status. Grading of malnutrition depends on anthropomorphic measures where z-scores > 2 standard deviations (SD) below the

mean of the reference population denote moderate to severe malnutrition. In Africa, an estimated 36% and 18% of children <5 years are classified as stunted or underweight, respectively (39% and 16% for Uganda, respectively). Malnutrition can alter drug absorption due to changes in gut integrity and gastric emptying; plasma binding of drugs; drug activation; and drug clearance. The net impact on overall PK exposure depends on both the drug and type of malnutrition. Clear specification of malnutrition indices and their relationship to

ACT	Modifying factor	Mode of modification	Change in PK exposure	Reinfection risk	Selected References
AL	EFV	Induce CYP/UGT	↓↓↓ AL	↑↑↑ AL	(17, 34, 63, 77, 78)
	Under-weight	↓ F, CYP	↓↓ AL	↑↑ AL	(51, 53, 64, 79)
	Stunted	↓ F, CYP	No data	Likely ↑	(80)

F: bioavailability, CYP: cytochrome p450, UGT: UDP-glucuronosyltransferases;

PK evaluations are needed to optimize drug protocols for malnourished children. Dosing of AL in malnourished children using weight-based guidelines that ignore nutritional status and a child's maturational age, may result in mg/kg doses that are too low in malnourished children. and worsen treatment outcomes.

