### 2.2 Secondary Objectives:

- 1) To assess the comparative safety of 5-day vs 3-day AL
- 2) To assess the impact of 3-day vs 5-day AL on the prevalence of gametocytemia following treatment
- 3) To evaluate the association of anthropomorphic indicators of malnutrition on PK exposure and outcomes of AL in HIV-infected and HIV-uninfected children.
- 4) To compare the diagnostic sensitivity of LAMP, HS-RDT, and microscopy for the detection of recurrent parasitemia.
- 5) To assess the comparative metabolomic profile of HIV-infected and HIV-uninfected children following treatment with 3-day and 5-day AL to assess
- 6) To assess the relationship between molecular markers of drug resistance and recurrent malaria

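### The nutrition groups in section 9.3 leave two sets of children unclassified, including those both stunted and underweight, and the plan does not say which analysis answers the nutrition objective

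*Combined protocol and SAP*

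**What the plan says.** The third secondary objective (section 2.2) is "To evaluate the association of anthropomorphic indicators of malnutrition on PK exposure and outcomes of AL" in HIV-infected and HIV-uninfected children. Section 9.3 introduces its groups "for a secondary study aim to relate nutritional status to PK and clinical outcomes". They are:

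- (a) stunted "but not underweight [i.e. height for age (HFA) z-score" at or below -2, with WFA above -2;
- (b) "underweight, but not stunted", meaning WFA at or below -2 with HFA above -2;
- (c) "of normal nutritional status (WFA and HFA z-scores" both above -1.

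Section 9.3 gives no rule for children outside these groups, no reason for leaving them out, and no expected group sizes.

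Three other places bear on the point. Section 9.2.2 lists associations of WFA and HFA with PK as a secondary outcome and names no groups. Section 9.5.2 tests weight, BMI, z-scores and arm circumference as stepwise covariates in the population PK model, and says indices of malnutrition will be examined for an effect on PD parameters. The Cox model in the same section is specified for the relation between drug exposure and recurrent infection; nutritional status is not named in it.

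On prevalence, section 1.1.9 states that in Africa "an estimated 36% and 18% of children <5 years are classified as stunted or underweight, respectively (39% and 16% for Uganda, respectively").

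**The concern.** The protocol's own rationale makes underweight children central. Section 1.1.7 reports that they have reduced AL exposure. Section 1.1.9 describes underweight as reflecting chronic and acute malnutrition together, and its table shows lower AL exposure for underweight children but no data for stunted ones. Section 9.3 then takes out of the underweight group every child who is also stunted, and puts that child in no other group. If the effect of malnutrition on exposure or recurrence is largest where both deficits are present, a comparison of groups (a), (b) and (c) cannot show it.

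The second gap, between mild deficit and normal, removes the middle of the distribution from the same comparison. What is at stake is how well a secondary objective is answered, and whether the choice between a grouped and a continuous analysis is fixed before the data are seen.

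**Working it through.** **Step 1. Do the groups cover every child?** Cut each z-score at -2 and -1 and apply section 9.3 as written.

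| | WFA ≤ -2 | WFA in (-2, -1] | WFA > -1 |
|---|---|---|---|
| HFA ≤ -2 | no group | a | a |
| HFA in (-2, -1] | b | no group | no group |
| HFA > -1 | b | no group | c |

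Four of the nine cells are empty. One is both z-scores at or below -2. The other three are neither z-score at or below -2 with at least one in (-2, -1]. This step needs no assumption.

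**Step 2. How many children?** The plan gives no figure to reproduce, so this is an estimate.

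From the documents: 39% stunted and 16% underweight in Uganda, both for children under 5 (section 1.1.9); a maximum of 380 children (section 3.2).

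Assumed: HFA and WFA bivariate normal with common SD of 1 or 1.2 and correlation r from 0 to 0.8. The documents give neither SD nor correlation.

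Means are set to reproduce the prevalences: mean = -2 - SD × Φ⁻¹(prevalence). With SD 1:

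- HFA mean = -2 + 0.279 = -1.721
- WFA mean = -2 + 0.994 = -1.006

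Then:

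- both = P(HFA ≤ -2 and WFA ≤ -2)
- a = 0.39 - both
- b = 0.16 - both
- c = P(HFA > -1 and WFA > -1)
- unclassified = 1 - a - b - c

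Worked case, SD 1 and r = 0:

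- both = 0.39 × 0.16 = 0.0624
- a = 0.3276 and b = 0.0976
- c = 0.2356 × 0.4978 = 0.1173
- unclassified = 1 - 0.3276 - 0.0976 - 0.1173 = 0.4575

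| SD | r | both | a | b | c | unclassified |
|---|---|---|---|---|---|---|
| 1 | 0 | 6.2% | 32.8% | 9.8% | 11.7% | 45.8% |
| 1 | 0.5 | 11.3% | 27.7% | 4.7% | 18.0% | 49.5% |
| 1 | 0.8 | 14.6% | 24.4% | 1.4% | 22.0% | 52.3% |
| 1.2 | 0 | 6.2% | 32.8% | 9.8% | 16.3% | 41.1% |
| 1.2 | 0.8 | 14.6% | 24.4% | 1.4% | 27.3% | 47.0% |

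**Step 3. What happens to underweight children?** The share left out of group (b) because they are also stunted is both / 0.16:

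- r = 0: 0.0624 / 0.16 = 39%
- r = 0.5: 0.1126 / 0.16 = 70%
- r = 0.8: 0.1464 / 0.16 = 92%

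Group (b) holds 0.0976 × 380 = 37 children at r = 0 and 0.0136 × 380 = 5 at r = 0.8, if all 380 are enrolled.

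**Step 4. Sensitivity to prevalence.** The trial enrols HIV-infected children aged 3 to 18 years and HIV-uninfected children aged 6 months to 18 years, so under-5 rates may not apply.

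- The all-Africa rates (36% and 18%) give 42.1% to 54.1% unclassified over the same SD and r range.
- An assumed 10% and 5% gives 28.5% (SD 1.2, r = 0.8) to 40.8% (SD 1, r = 0).
- A population at the reference mean (SD 1, r = 0.5 to 0.8) gives 19% to 22%.

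**The case against.** The strongest reply is that section 9.3 only characterises children. It names no test, no model and no exclusion. The listed secondary outcome uses WFA and HFA without groups, and Table 8 contains no nutritional comparison. Section 9.5.2 puts special focus on malnutrition markers, tests linear and nonlinear covariate relations, and extends the question to PD parameters, with no restriction to the three groups. This largely stands. A reader might infer that the unlabelled children are discarded and the objective answered only on a selected subset. The documents do not support that: these children lack a label and drop out only of an analysis that uses the labels.

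Three further inferences also go too far.

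- That about half of all children are unclassified, as a fact. The figure depends on under-5 prevalences and on an assumed distribution, SD and correlation.
- That every child with a z-score between -2 and -1 is unclassified. A child with HFA at or below -2 and WFA of -1.5 is in group (a).
- That the underweight-only group will be too small to analyse. The calculation gives about 5 to 37 children, the plan sets no minimum, and adding categories would not enlarge the group.

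It can also be argued that isolated phenotypes, with a buffer before normal, suit section 1.1.9's interest in the type of malnutrition. That is plausible, but the protocol does not give it as a reason, and it would not explain having no category for children with both deficits.

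The reply does not settle which analysis answers the objective. Section 9.3 is the only section devoted to classifying nutritional status, and it states that its purpose covers clinical outcomes. Stepwise selection may leave a z-score out of the final PK model, and the Cox model is written for drug exposure.

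**Conclusion.** The concern holds in this form. The two gaps in section 9.3 are certain from the text, and any analysis by these groups omits the children who are most malnourished on the two indices used. The plan does not say whether that grouped analysis or the section 9.5.2 covariate work answers the nutrition objective.

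The size is an estimate. At the protocol's Ugandan under-5 rates, about 41% to 52% of children are unclassified, 39% to 92% of underweight children are left out because they are also stunted, and the underweight-only group is about 1% to 10% of the sample. These figures rest on bivariate normal z-scores, SD 1 to 1.2 and correlation 0 to 0.8. At an assumed 10% and 5%, as might apply in older children, roughly 28.5% to 41% are unclassified. The consequence is confined to a secondary objective; neither primary outcome is affected.

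**What to change.** State in the analysis plan that continuous HFA and WFA z-scores, in all children, are the main nutrition exposure, both in the PK model and in the Cox model for recurrence. Report their estimated effects whether or not stepwise selection would keep them.

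If groups are also reported, add two: both stunted and underweight (both z-scores at or below -2), and mild (neither z-score at or below -2, at least one in -2 to -1). Every child is then classified. At the Ugandan rates and under the assumptions above, the added groups would hold about 6% to 15% and 32% to 40% of children.

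The cost is SAP wording and slightly more analysis. Section 6.5 already has height, weight, age and arm circumference recorded at each enrolled episode, and section 9.5.2 already plans robust standard errors for repeated episodes, so no new data or visits are needed.
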